**MATERNAL POSITIONS IN ELECTRONIC FETAL MONITORING: IMPACT AND
EVALUATION**

Trial registration: In addition, clinical trials were registered (ClinicalTrials.gov ID: NCT05863156).

The American College of Obstetricians and Gynecologists (ACOG) states that electronic fetal monitoring can be conducted in the semi-Fowler position, where the individual lies on their back with their head elevated at a 30-degree angle, or in the sitting or lateral side-lying position.⁸ The woman's position during EFM greatly influences the indication of fetal reactivity.⁴ Few articles in the literature focus on less commonly used positions and assess the utilization and effects of right and left lateral positions, semi-Fowler positions, and sitting positions.¹ Emphasis has been placed on the need for investigations into different positions to ensure maternal comfort, maternal, and fetal well-being.^{4,10} Thus, this study was conducted to evaluate the impact of various positions on maternal comfort, maternal blood pressure, and fetal health during antenatal electronic fetal monitoring.

Research Hypotheses:

H1: The semi-Fowler position during electronic fetal monitoring will result in significantly higher maternal comfort compared to the left lateral and right lateral positions.

H2: The semi-Fowler position will result in a significantly shorter duration of cardiotocography (CTG) compared to the left lateral and right lateral positions.

H3: The semi-Fowler position will produce statistically significant improvements in fetal health indicators, such as fetal heart rate accelerations and fetal movements, during CTG compared to the left lateral and right lateral positions.

H4: Maternal systolic and diastolic blood pressure will vary significantly based on the maternal position during CTG, with the semi-Fowler position providing a more stable blood pressure profile than the left lateral and right lateral positions.

Methods

Study Design: This study was conducted at the pregnancy monitoring polyclinic of an obstetrics hospital in Istanbul between December 2021 and January 2023. It employed an experimental design as a randomized controlled trial with two intervention groups and one control group to evaluate the impact of maternal and fetal health based on the position of the pregnant woman during electronic fetal monitoring. The study analysis followed the Consolidated Standards of Reporting Trials (CONSORT) reporting guideline.

Study Population: The study's universe consisted of 12.000 individuals registered for electronic fetal monitoring at a hospital obstetrics polyclinic in the last year. The G*Power 3.1.9.4 program was used to calculate the study sample size. Calculations indicated an effect size of $d:0.5$ (medium) at a confidence interval (CI) of 95%. The sample size was initially set at 210 individuals but was increased by 15% to 240 to account for potential participation refusals.

Randomization: Participants were assigned to intervention and control groups using a computer-generated random sequence from random.org(www.randomizer.org). Allocation concealment was maintained by an independent researcher who was not involved in the data collection process. A total of 240 participants were randomly allocated into three groups: 60 participants in the right lateral position (Intervention 1), 60 in the semi-Fowler position (Intervention 2), and 120 in the left lateral position (Control group).

Inclusion Criteria: Participants met several inclusion criteria, including being over the age of 18, aged 35 or younger, in the late third trimester (34th-40th gestational week), having fetal biometric measurements corresponding to the 34th-40th gestational week, having a single fetus, no maternal or fetal risk factors affecting pregnancy, normal vital signs before the procedure, not fasting for more than 2 hours before the procedure, and accepting the suggested positioning.

Data Collection Tools:

Information Questionnaire: This questionnaire comprised 35 items covering the pregnant women's sociodemographics, obstetric data, vital signs (blood pressure-BP, pulse, temperature, and oxygen saturation-SPO₂) before, during, and after CTG. It also included fetal monitoring findings assessed four times during the procedure (at 0-5 min., 6-10 min., 11-15 min., 16-20 min.) along with the position of the pregnant woman.

General Comfort Questionnaire-Short Form (GCQ-SF): Developed by Kolcaba in 2006, this questionnaire measures comfort across sub-dimensions of relief, ease, and transcendence. It contains both positive and negative items, with negative items scored in reverse. Scores are calculated by dividing the total score by the number of items, resulting in values between 1 (low comfort) and 6 (high comfort).¹¹⁻¹³

Procedure: Electronic fetal monitoring at the hospital was performed by midwives and nurses, with each session lasting 20 minutes. Pregnant women were assigned numbers upon arrival, and random assignment to groups was done with the support of an independent clinic midwife and nurse, ensuring a single-blinded design. The same midwife and nurses conducted all procedures throughout the study.

The intervention group, comprising 120 pregnant women, was further divided into two subgroups: 60 women were assigned to the right lateral position (Intervention 1), and 60 women to the semi-Fowler position (Intervention 2). The positions were explained to the participants, and vital signs were monitored at regular intervals before, during, and after the CTG procedure.

The control group, also consisting of 120 women, adhered to the clinic's routine practice of the left lateral position. All women in this group were placed in the left lateral position, with the remainder of the procedure conducted in the same manner as for the intervention groups. Researchers supervised all monitoring and follow-up assessments (Figure 1).

Fig. 1. CONSORT flow diagram.

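### The total of 210 for d = 0.5 is not reconciled with the 60/60/120 allocation, and semi-Fowler versus right lateral (60 v 60) is smaller than the calculation requires

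*Protocol*

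**What the plan says.** The sample-size basis is in the protocol's Study Population section. "The G*Power 3.1.9.4 program was used to calculate the study sample size", followed by "Calculations indicated an effect size of $d:0.5$ (medium) at a confidence interval (CI) of 95%. The sample size was initially set at 210 individuals". The total was then raised to 240 for refusals. No power, alpha, sidedness, test or number of groups is given.

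The Randomization section allocates "60 participants in the right lateral position (Intervention 1), 60 in the semi-Fowler position (Intervention 2"), with the remaining 120 in the left lateral control group. The Procedure section presents the same allocation as two halves, one of them later split: "The intervention group, comprising 120 pregnant women, was further divided into two subgroups" of 60, beside a control group of 120.

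Under Research Hypotheses, H1 expects the semi-Fowler position to give "significantly higher maternal comfort compared to the left lateral and right lateral positions". H2, H3 and the second part of H4 (the more stable blood pressure profile) use the same two comparators. The first part of H4 says that blood pressure varies with position, which is a three-group question and is not part of this point. No hypothesis compares the combined 120 intervention women with the 120 controls.

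**The concern.** Cohen's d is an effect size for two groups, and 210 is the total that a common two-group calculation returns for d = 0.5. The trial has three arms, and two of them hold 60 women. If 210 was a two-group total, the calculation was made for a comparison that the hypotheses do not contain and was not redone when one side was divided.

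The interpretation of a null result is at stake. The protocol presents the trial as sized for a medium effect. A reader who meets a non-significant semi-Fowler v right lateral result may then take it as evidence against a medium difference, although that contrast is the smallest in the design. Because the power is not printed, the reader cannot correct for this.

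**Working it through.** **Inputs.** From Study Population: d = 0.5, 95%, total 210, raised to 240. From Randomization: 60 right lateral, 60 semi-Fowler, 120 left lateral. Assumed, because not stated: a two-sample t-test with equal SDs, no adjustment for multiple contrasts, and alpha 5% (taken from the 95%). Sidedness and power were varied.

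**Formula.** Power = P(T > t_crit), where T is noncentral t with n1 + n2 − 2 degrees of freedom and noncentrality d × √[n1·n2/(n1 + n2)].

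**Step 1: reproduce 210.**
- *Reading A, two groups, two-sided 5%, 95% power.* At 105 v 105 the noncentrality is 0.5 × √52.5 = 3.62 and power is 0.9501. At 104 v 104 it is 0.9483. So 105 per group, and 2 × 105 = 210.
- *Reading B, three groups, one-sided 5%, 90% power per pair.* At 70 v 70 the noncentrality is 0.5 × √35 = 2.96 and power is 0.903. At 69 v 69 it is 0.899. So 70 per group, and 3 × 70 = 210.
- *Near match.* A three-group one-way ANOVA with f = 0.25 at 90% power needs 207. The protocol gives d, not f, and 207 is not 210.
- *No match.* Three equal groups with a two-sided t-test need 192, 219, 258 or 315 at 80%, 85%, 90% or 95% power.

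**Step 2: power of the hypothesised contrasts at d = 0.5, all 240 analysed.** The equal-group equivalent of n1 v n2 is 2·n1·n2/(n1 + n2) per group.

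| Contrast | Equal-group equivalent | Two-sided 5% (A: target 95%) | One-sided 5% (B: target 90%) |
|---|---|---|---|
| Semi-Fowler v right lateral, 60 v 60 | 60 | 77.5% | 86.0% |
| Semi-Fowler v left lateral, 60 v 120 | 80 | 88.2% | 93.4% |

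Reading A requires 105 per group and reading B requires 70. The first contrast (60) misses both. The second (80) misses A and meets B.

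**Step 3: both contrasts significant.** By simulation (400,000 runs, semi-Fowler 0.5 SD better than two equal laterals, two-sided 5%), both reach significance in 73% of trials.

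**Step 4: only about 210 analysed.** With 52 right lateral, 53 semi-Fowler and 105 left lateral, two-sided power is about 84% against left lateral, 72% against right lateral and 66% for both.

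**Step 5: effect detectable with 95% power, two-sided.** d = 0.57 for 60 v 120 and d = 0.66 for 60 v 60.

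**Step 6: the pooled comparison.** Combined intervention v control (120 v 120) has 97.1% power for d = 0.5 and is the only comparison that meets the size in reading A. It does not serve H1-H3, because it mixes semi-Fowler with one of its own comparators. If semi-Fowler is 0.5 SD better than two equal laterals, the pooled difference is (0.5 + 0)/2 = 0.25 SD, and power is 49%.

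**The case against.** The strongest reply is that the protocol never states 95% power, so a shortfall measured against 95% is the reviewer's construction. Reading B reproduces 210 just as exactly, uses d, has three groups and suits the directional wording of H1-H3. On that reading semi-Fowler v left lateral exceeds its target and still has 90.5% power if it is 53 v 105. All of this stands. A reader might infer that no contrast in H1-H4 has the size the calculation requires, or that the protocol promises 95% power. The documents support neither: the left lateral contrast is adequate under reading B, the three-group part of H4 is a different question, and no power is printed.

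The 120/120 presentation in the Procedure section suggests a two-group origin but is weak evidence for it, since half of 240 is 120 under any derivation. The joint 73% applies only if both comparisons must succeed, and the hypotheses do not say so explicitly. By an 80% standard, the left lateral contrast is sufficient on either basis, and the right lateral contrast misses only narrowly when tested two-sided.

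It could also be said that a statistical analysis plan may give the inputs. It may. But the total, the allocation and the hypotheses all stand in this protocol and do not fit one another there, and a confidence level alone cannot produce a sample size.

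The reply does not remove the 60 v 60 contrast: it is below the size required under both readings that give exactly 210, and also below the 69 per group of the ANOVA near match.

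**Conclusion.** The point holds in a limited form. The protocol's 210 rests on inputs it does not state and was not reconciled with the 60/60/120 allocation. Semi-Fowler v right lateral, which all four hypotheses name, is smaller than the calculation requires: 77.5% against 95% on the two-sided two-group reading, 86.0% against 90% on the one-sided three-group reading. Under these the chance of missing a true d = 0.5 is 22.5% or 14.0%. For semi-Fowler v left lateral the conclusion depends on the reading: short on the first, met on the second.

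The two-group origin is the closest reading, since d is a two-group measure and the match is exact, but it remains an inference for the sponsor to confirm. The figures assume t-tests, equal SDs, all 240 women analysed and no multiplicity adjustment. Bonferroni for two contrasts (two-sided 2.5% each) would lower them to 81.6% against left lateral and 68.0% against right lateral. Correction is worthwhile, because this is the only planning figure in the protocol; it does not invalidate the design.

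**What to change.** In Study Population:

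1. Replace "at a confidence interval (CI) of 95"% with the test, sidedness, alpha, power and number of groups actually entered in G*Power, as confirmed by the sponsor. A derivation reconstructed by a reviewer should not be inserted in their place.
2. Add the power that 60/60/120 delivers for d = 0.5 at two-sided 5% with all 240 analysed: 88% against left lateral, 78% against right lateral, 73% if both must be significant. Give 84%, 72% and 66% for about 210 analysed, and the effects detectable with 95% power: d = 0.57 against left lateral and 0.66 against right lateral. If the confirmed test is one-sided, give the one-sided figures as well.
3. State that a non-significant semi-Fowler v right lateral result does not by itself exclude d = 0.5 and will be read from its confidence interval.
4. State that the combined 120-woman intervention group is not the comparison for H1-H3.

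The cost is wording, and a stated power that looks less favourable. No additional women, visits or procedures are needed.

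### H2 predicts a shorter CTG in the semi-Fowler position, but the Procedure sets every session at 20 minutes, so as written H2 has no outcome that can vary

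*Protocol*

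**What the plan says.** Four statements in the Protocol bear on this point.

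- **Research Hypotheses, H2:** "The semi-Fowler position will result in a significantly shorter duration of cardiotocography (CTG) compared to the left lateral and right lateral positions".
- **Procedure, opening sentence:** "Electronic fetal monitoring at the hospital was performed by midwives and nurses, with each session lasting 20 minutes".
- **Procedure, control group:** women were placed in the left lateral position, "with the remainder of the procedure conducted in the same manner as for the intervention groups".
- **Data Collection Tools, Information Questionnaire:** "fetal monitoring findings assessed four times during the procedure (at 0-5 min., 6-10 min., 11-15 min., 16-20 min".

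The aim at the end of the background is to "evaluate the impact of various positions on maternal comfort, maternal blood pressure, and fetal health during antenatal electronic fetal monitoring"; duration is not part of it. The document does not define CTG duration, and it gives no rule for ending a session early or extending it.

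**The concern.** A hypothesis about duration needs a duration that can differ between women. The Procedure gives every session the same length, and nothing in the text exempts an arm. The hypothesis and the procedure that should generate its data therefore contradict each other.

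Two things are at stake. First, one of the four formal hypotheses cannot be answered under the procedure as described. If a difference in duration were reported, a reader could not tell what had been measured: time on the monitor, time to some feature of the trace, or something else. Second, if session length did vary by position, the 20-minute statement is wrong. Raw counts of accelerations and movements under H3 would then be taken over unequal observation times. No statement in the protocol says that this happened, so the second point is conditional and no size is attached to it.

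**Working it through.** The protocol gives no mean, SD or target difference for duration, so there is no figure to reproduce. This is a consistency check on the text, and the arithmetic only spells out what the text implies.

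**Inputs**

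| Item | Value | Source in Protocol |
|---|---|---|
| H2 outcome | CTG duration, semi-Fowler against each lateral position | Research Hypotheses |
| Session length | 20 min for each session | Procedure |
| Handling across arms | Same apart from position | Procedure, control group |
| Recording windows | 0-5, 6-10, 11-15, 16-20 min | Information Questionnaire |
| Arm sizes | 60 semi-Fowler, 120 left lateral, 60 right lateral | Randomization |

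**Step 1: do the windows agree with the session length?** The last of the four windows ends at 20 minutes, which matches the Procedure. The windows do not prove that recording stopped there, but they leave no sign of a session that was shorter or longer.

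**Step 2: what does H2 compare under the literal text?** Duration is 20 for all 60 + 120 + 60 = 240 women. Each arm mean is 20 and each arm SD is 0.

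- Semi-Fowler minus left lateral (60 vs 120): 20 − 20 = 0
- Semi-Fowler minus right lateral (60 vs 60): 20 − 20 = 0
- Standard error = √(SD₁²/n₁ + SD₂²/n₂) = √(0 + 0) = 0 for both
- Test statistic = 0/0, undefined for both

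**Step 3: does another reading of the text rescue H2?**

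| Reading | Stated in the protocol? | Consequence if true |
|---|---|---|
| 20 minutes is nominal | No | The 20-minute statement needs correcting |
| Some women had more than one session | No; a single set of four windows is described | The number of sessions is the real outcome, and H2 must say so |
| Duration means time to a satisfactory or reactive trace | No | H2 needs that definition and a criterion |

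Every row requires a change either to H2 or to the 20-minute sentence.

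**Step 4: how far does it reach?** It affects 1 of 4 hypotheses. Study Population does not link the sample size to duration, so the planned numbers are unaffected.

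**The case against.** The strongest reply is that the contradiction rests on one sentence. That sentence describes how monitoring is done at the hospital and may give the clinic's usual session length, not an exact time for each participant. Equal handling across arms does not by itself mean equal elapsed time, and the windows say when findings were assessed, not when recording ended. The operational definition of duration could also sit in a statistical analysis plan that is not at hand, or among the 35 questionnaire items, which are described only by topic.

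Part of this stands. The supporting statements are consistent with a fixed length but do not independently prove it. It cannot be concluded that duration went unrecorded, or that it truly never varied. The zero-variance arithmetic restates the conflict and is not evidence about the data.

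The conflict itself remains. The sentence opens the trial's own Procedure and speaks of each session without qualification. An analysis plan can define how an outcome is analysed, but it cannot make a quantity vary that the procedure holds constant. If the 20 minutes was only nominal, the protocol misdescribes its procedure and still needs correcting.

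**Conclusion.** The concern holds as a contradiction within the protocol. Followed as written, H2 has no outcome that can vary: both contrasts are 0 minutes with zero variance, and one of the four hypotheses cannot be tested. This rests on taking the 20-minute statement at its word for all three arms. If sessions actually varied, H2 might be testable, but the protocol would then be wrong about session length, and H3 would need attention to observation time.

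It should be fixed, but it is not critical. H1 and H4 are unaffected, duration lies outside the stated aim, and the sample size does not depend on H2. Confidence in the textual conflict is high; what was actually done with session length cannot be known from the document.

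**What to change.** Reconcile H2 with the Procedure in whichever of these ways matches what was done. None of them involves deciding how long monitoring ought to last.

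- **(a) Sessions were fixed.** Withdraw H2 as untestable and say so openly. Cost: wording and disclosure only.
- **(b) Sessions were fixed, but a timing question is still wanted.** Replace duration with an outcome that can vary within the session, for example the first 5-minute window in which a stated reactivity criterion is met, censored at 20 minutes. Compare semi-Fowler with each lateral position. This is optional and depends on the recorded window findings including what the criterion needs, which the protocol does not show. Resolution is coarse: four windows plus one censored category give 5 possible values. The study ran "between December 2021 and January 2023", so an outcome defined after data collection must be labelled post hoc.
- **(c) Session length varied.** Correct the 20-minute statement, report how duration was measured and what ended a session, and compare the H3 indicators over the observation time common to all women or per minute observed. This is possible only if duration was recorded. Cost: wording and disclosure, plus the adjusted H3 comparison.

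Option (a) or (c) alone is enough to remove the contradiction.
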